4.3.6 Coding dictionaries

AEs, medical history, and procedures are to be coded using the Medical Dictionary for Regulatory Activities (MedDRA) Version 27.0 or later. Previous and concomitant treatments are to be coded using the World Health Organization Drug Dictionary Enhanced (WHO DDE) dated 01MAR2024 or later (format B3).

5 SUBJECT DISPOSITION

5.1 Disposition

The number and percentage of subjects screened and included in each of the analysis sets will be summarized overall. The number and percentage of subjects who completed or discontinued from the study treatment and from study will also be presented, with the reason for discontinuation. All percentages will be based on the number of subjects in the safety set.

Reasons for screen failure will be listed only.

5.2 Protocol deviations

A protocol deviation is any change, divergence, or departure from the study design or procedures defined in the protocol. Protocol deviations will be documented by the clinical monitor throughout the course of monitoring visits. The protocol deviations will be categorized as important and non-important deviations.

All protocol deviations will be listed.

5.3 Inclusion and exclusion criteria

Full inclusion and exclusion criteria are listed in protocol Section 3.3.1 and 3.3.2, respectively. Unmet inclusion and met exclusion criteria for each subject will be listed.

6 DEMOGRAPHICS AND BASELINE CHARACTERISTICS

6.1 Demographics and general baseline characteristics

The following demographics and baseline characteristics data will be presented in tables using descriptive statistics for the Safety, PK, and PD sets:

- Age, sex, childbearing potential, race, ethnicity
- Height, weight, and BMI.

6.2 Medical history

Medical history will be listed.

7 TREATMENTS AND MEDICATIONS

7.1 Prior and concomitant medications

Prior medications are defined as medications with a stop date prior to the first dose of study drug. Concomitant medications are defined as medications that are either ongoing at the start of the first dose of study drug or start after the start of the first dose of study drug.

Prior and concomitant medications will be listed separately.

7.2 Study treatments

Exposure to study treatment will be listed.

8 PHARMACOKINETIC ANALYSIS

8.1 Plasma concentration

Plasma concentrations of pitavastatin, pitavastatin lactone, ceftobiprole, and CP-I will be analyzed at each time point of collection and will be summarized with descriptive statistics (n, mean, SD, coefficient of variation [CV%], minimum, median, maximum, and geometric mean) for the PK set (pitavastatin, pitavastatin lactone, and ceftobiprole) or PD set (CP-I).

Treatment of outliers

Individual concentration-time points, if considered anomalous, may be excluded from the analysis at the discretion of the pharmacokineticist and with approval from the Sponsor following a review of the available documentation. Any such exclusion will be outlined in the CSR.

Entire individual treatment profiles for a subject may be excluded following review of the available documentation. However, PK analyses may be performed with and without the excluded profiles. Any such exclusion will be clearly listed along with justification for exclusion.

Non-quantifiable concentrations

All concentration values reported as no results (not collected or not determined) values will be treated as missing. For the calculation of concentration summaries, all concentrations below the quantifiable limit (BLQ) will be treated as 0. Values that are BLQ will be displayed as 'BLQ' in listings.

Plasma concentrations will also be summarized with following figures:

- Plot of individual concentrations versus actual sampling time, using linear and semi-log scale by treatment period.
- Combined individual plasma concentrations versus actual sampling time, using linear and semi-log scale by treatment period.
- Plot of geometric mean versus scheduled sampling time, using linear and semi-log scale by treatment period.
- Boxplot of geometric mean versus scheduled sampling time by treatment period.

8.2 PK parameters

Individual PK parameters will be estimated using non-compartmental methods with WinNonlin[®].

The plasma PK parameters will be estimated from the concentration-time profiles. In estimating the PK parameters, BLQ values at the beginning of the profile will be set to zero. BLQ values that occur after the first quantifiable point will be considered missing. Values that are embedded between BLQs, or quantifiable values occurring after two or more BLQs, will be set to missing at the discretion of the pharmacokineticist and in agreement with the Sponsor. Actual sampling times, rather than scheduled sampling times, will be used in all computations involving sampling times. If the actual time or dose time is missing, the scheduled time may be substituted in order to calculate the PK parameter.

The PK parameters to be determined or calculated using noncompartmental analysis from the plasma concentration-time data are:

- For pitavastatin and pitavastatin lactone on Day 1 and Day 6: C_{max} , t_{max} , k_{el} , $t_{1/2}$, AUC_{0-t} , AUC_{0-inf} , AUC_{extrap} , adjusted R-squared, CL/F (pitavastatin only), V_z/F (pitavastatin only), as appropriate; ratios of C_{max} , AUC_{0-t} , and AUC_{0-inf} of pitavastatin lactone over parent drug; AUC and C_{max} ratio Day 6/Day 1 for pitavastatin and pitavastatin lactone.
- For ceftobiprole on Day 5 and Day 6: C_{trough} , C_{max} , t_{max} , k_{el} , $t_{1/2}$, AUC_{0-8h} , AUC_{extrap} , adjusted R-squared, CL, and V_z , as appropriate.

Following administration, C_{max} and t_{max} will be obtained directly from the experimental observations. If multiple maxima occur at equal concentrations, the first temporal value will be taken. AUC will be calculated using the linear up/log down trapezoidal rule, using actual elapsed time since the start of administration. The number of data points included in the regression of k_{el} and $t_{1/2}$ after single dose will be determined by visual inspection, but a minimum of 3 data points in the terminal phase, excluding C_{max} , will be required to estimate k_{el} . The k_{el} values (and consequently $t_{1/2}$, CL/F, V_z/F , AUC_{0-inf}) will be considered unreliable estimates if the period of time is over which an individual k_{el} was estimated is less than twice the resultant $t_{1/2}$ or if the adjusted coefficient of determination R-squared is less than or equal to 0.75.

The proportion of AUC_{0-inf} due to extrapolation (AUC_{extrap}) will also be calculated and expressed as a percentage. The value of AUC_{extrap} should be less than or equal to 20% for

AUC_{0-inf} to be considered to be well estimated. If AUC_{extrap} is higher than 20%, then the values of AUC_{0-inf}, CL/F, and V_z/F will be considered unreliable and therefore excluded from the summaries.

All PK parameters will be summarized with descriptive statistics (n, mean, SD, CV, minimum, median, maximum, geometric mean, and geometric CV) for the PK set. For t_{max}, only n, median, minimum and maximum will be presented. All parameters will be listed by subject and period, parameters that meet the inclusion criteria for PK analysis will be accompanied by an indication that each criteria is met.

A scatter plot of individual (plus mean and median) PK parameters C_{max}, AUC_{0-t} and AUC_{0-inf} by treatment (i.e., without or with ceftobiprole) for pitavastatin and pitavastatin lactone will be provided.

A mixed-effects model with subject as a random effect and treatment (i.e., without or with ceftobiprole) as a fixed effect will be performed on the following natural logarithm (ln)-transformed PK parameters of pitavastatin and pitavastatin lactone: C_{max}, AUC_{0-t}, and AUC_{0-inf}. From this model, the back-transformed least-squares means (LSMeans) for each treatment will be presented. The ratio of least-squares geometric means between the test treatment (coadministration of pitavastatin + ceftobiprole) to the reference (pitavastatin alone) and the corresponding 90% confidence interval (CI) will be presented.

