- i. Blood sampling for PK of pitavastatin and its metabolite pitavastatin lactone in plasma on Day 1 (before pitavastatin dosing and 0.25, 0.5, 0.75, 1, 1.5, 2, 2.5, 3, 4, 6, 8, 10, and 12 hours after pitavastatin dosing), Day 2 (24 and 36 hours after pitavastatin dosing), and Day 3 (48 hours after pitavastatin dosing), and on Day 6 (before pitavastatin dosing and 0.25, 0.5, 0.75, 1, 1.5, 2, 2.5, 3, 4, 6, 8, 10, and 12 hours after pitavastatin dosing), Day 7 (24 hours and 36 after pitavastatin dosing), and Day 8 (48 hours after pitavastatin dosing). Note: [Table 2](#) provides the PK sampling time points relative to Day 1 pitavastatin administration.
- j. Blood sampling for ceftobiprole PK in plasma on Day 4: predose and 2 hours (immediately after infusion stop) after start of the first infusion on Day 4; on Day 5: predose and 1, 2 (immediately after infusion stop), 4, 6, and 8 hours (predose prior to the second infusion on Day 5) after start of the first infusion on Day 5; on Day 6 (predose), and 1, 2 (immediately after infusion stop), 4, 6, and 8 hours (predose for the second infusion on Day 6) after start of the first infusion on Day 6, and on Day 7 (predose, prior to the first infusion on Day 7). Note: [Table 2](#) provides the PK sampling time points relative to Day 1 pitavastatin administration.
- k. Blood sampling for OATP1B activity marker CP-I in plasma: on Day 5 prior to the start of the first ceftobiprole infusion in the morning, at 2, 4, 6, and 8 hours after the start of the first ceftobiprole infusion on Day 5 (8-hour sample just prior to the start of the second ceftobiprole infusion), at 16 hours after the start of the first ceftobiprole infusion on Day 5 (just prior to the start of the third ceftobiprole infusion on Day 5), and prior to pitavastatin dosing on Day 6 (approximately 25.5 hours after the start of the first ceftobiprole infusion on Day 5) (total of 7 samples). On Day -1 and Day 1, a total of 7 samples will be taken at the corresponding clock times as are planned for Day 5 and Day 6. Note: [Table 2](#) provides the sampling time points relative to Day 1 pitavastatin administration.

**Table 2 Detailed Schedule of Administration of Pitavastatin and Ceftobiprole, and Assessments With Time Points Relative to Day 1 Pitavastatin Dosing**

Day	Time Point With Day 1 Pitavastatin Dosing as Baseline (hours)	Dose	PK of Pitavastatin and Metabolite	Ceftobiprole PK	CP-I Blood Sampling	12-Lead ECG	Vital Signs
Screening						X	X
-2						X	X

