### 3.4.5 Timing of Doses in the Study

On Day 1 and Day 6, pitavastatin will be administered to subjects between 08:00 and 12:00 hours in the morning under fasted conditions. Subjects will fast overnight for at least 10 hours following a light supper.

The study drug will be swallowed together with approximately 240 mL water (room temperature). The study drug should not be chewed.

On Days 4 to Day 7, ceftobiprole will be administered as a 2-hour iv infusion 3 times a day every 8 hours (q8h). The morning dose will be administered following an overnight fast of at least 10 hours.

On Day 6, a single oral dose of pitavastatin will be coadministered the morning with a single iv dose of dose of ceftobiprole under fasted conditions. Pitavastatin will be administered 30 minutes prior to the end of the 2-hour ceftobiprole infusion.

On Days 1 and 6 only, fasting will continue for a period of 4 hours after administration of pitavastatin, i.e., until scheduled lunch. On Days 4, 5 and 7, a non-standardized breakfast will be given 1 hour after the end of the first ceftobiprole infusion of that day.

During fasting, no fluids are allowed except water, with the following exception. On Days 1 and 6, water is not allowed from 1 hour before administration of pitavastatin until 1 hour after administration of pitavastatin (apart from the water taken with the dose as described above).

- On Days 4 to 7, water is not allowed from 1 hour before the start of the first ceftobiprole infusion until 1 hour after the end of the first ceftobiprole infusion.

When not fasting, noncaffeinated fluids are allowed ad libitum.

On PK days (Day 1, Day 5, and Day 6) dosing for each individual subject will be at around the same time ( $\pm 15$  minutes) on each dosing day. On other (non-PK) days, a margin of  $\pm 30$  minutes is allowed.

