#### **3.5.2.1 Timing of Assessments**

For pitavastatin PK, predose samples will be obtained between waking up and dosing. Postdose samples up to 20 minutes postdose will be obtained with a time window of ±1 minute. Thereafter, postdose samples will be obtained with time margins of ±5% of the time that has passed since dosing.

For ceftobiprole PK, samples prior to the first infusion of a day will be obtained between waking up and the start of the iv infusion. For predose (trough) samples during multiple dosing, a 5% time

window since the last dose is allowed, but the sample must be taken before the next dose. Postdose samples up to 20 minutes after the start of the iv infusion will be obtained with a time window of  $\pm 1$  minute. Thereafter, postdose samples will be obtained with time margins of  $\pm 5\%$  of the time that has passed since the start of the iv infusion.

For CP-I diurnal profiling on Days -1 to 1 and on Days 5 to 6, samples will be obtained within margins of  $\pm 15$  minutes. On Day 5, the first sample will be obtained prior to the start of the iv infusion with ceftobiprole. On Days 1 and 6, the last CP-I sample will be collected prior to pitavastatin dosing.

For safety assessments, predose assessments will be performed between waking up and dosing / the start of the iv infusion. For safety assessments up to 2.5 hours postdose/after the start of the iv infusion, a time window of  $\pm 15$  minutes is allowed. Thereafter, serial postdose assessments (e.g., multiple assessments within any given day) must be performed with time margins of  $\pm 10\%$  of the time that has passed since (last) dosing/the start of the iv infusion.

When assessments are planned for the same scheme time, the order of the assessments should be arranged in such a way that PK and PD blood sampling will be done after the ECG and vital signs recordings have been conducted, with PK blood sampling exactly on time.

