2.2 Secondary objectives

The secondary objectives are:

- To assess the pharmacodynamic (PD) effect of iv ceftobiprole on the diurnal plasma level profile of coproporphyrin I (CP-I) in healthy subjects
- To describe the systemic exposure of iv ceftobiprole without and with oral administration of pitavastatin in healthy subjects
- To assess the single-dose plasma PK of the pitavastatin metabolite, pitavastatin lactone, after a single oral dose of pitavastatin, administered without and with iv ceftobiprole in healthy subjects
- To assess the safety and tolerability of ceftobiprole without and with administration of a single oral dose of pitavastatin in healthy subjects.

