3.1.3 Treatments

The following treatments are planned to be administered in two periods:

- Period 1 (from Day -1 to Day 3): pitavastatin single dose
 - Day 1: a single oral dose of 2 mg pitavastatin is administered in the morning under fasted conditions.
- Period 2 (from Day 4 to Day 8): pitavastatin single dose + ceftobiprole every 8 hours (q8h)
 - Day 4 to Day 7: 500 mg ceftobiprole (as the prodrug ceftobiprole medocaryl sodium) is administered as a 2-hour iv dose q8h under fasted conditions in the morning, and irrespective of timing of food intake further on the day.
 - Day 6: a single oral dose of 2 mg pitavastatin is coadministered with ceftobiprole 30 minutes prior to the end of the first iv dose of 500 mg ceftobiprole under fasted conditions.

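### Day 6 ceftobiprole predose C_trough cannot, and C_max hardly can, reflect a tablet taken 1.5 h into the infusion; AUC0-8h is diluted and C_trough is not tied to a sample

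*SAP*

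**What the plan says.** A secondary objective (SAP 2.2, protocol section 2) is "To describe the systemic exposure of iv ceftobiprole without and with oral administration of pitavastatin in healthy subjects". SAP 8.2 addresses it with C_trough, C_max, t_max, k_el, t1/2, AUC0-8h, CL and V_z, "For ceftobiprole on Day 5 and Day 6". Day 5 is the day without pitavastatin and Day 6 the day with it.

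Pitavastatin on Day 6 is given "30 minutes prior to the end of the first iv dose of 500 mg ceftobiprole" (SAP 3.1.3; protocol 3.4.5 agrees). Protocol Table 2 puts the infusion start at 118.5 h, the tablet at 120 h and the infusion end at 120.5 h.

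Ceftobiprole is sampled "on Day 6 (predose), and 1, 2 (immediately after infusion stop), 4, 6, and 8 hours (predose for the second infusion on Day 6"), "and on Day 7 (predose, prior to the first infusion on Day 7") (protocol Table 1, footnote j). Protocol Table 3 ends AUC0-8h at 8 h after the start of the first infusion, and SAP 8.2 counts time from the start of administration.

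Table 3 only spells out what C_trough stands for, and SAP 8.2 does not define it. The nearest guidance is a sampling window in protocol 3.5.2.1, "For predose (trough) samples during multiple dosing". No listed parameter uses the Day 7 sample, although SAP 8.1 summarises ceftobiprole concentrations at every collection time.

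**The concern.** A comparison of exposure without and with a second drug needs parameters that the second drug had time to change. Here the tablet comes three quarters of the way through the infusion that defines Day 6. Some of the listed parameters are settled, or nearly settled, by then.

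If Day 5 and Day 6 C_trough and C_max turn out alike, a reader of the study report may take that as evidence that pitavastatin leaves ceftobiprole unchanged. The timing would produce most of that similarity whatever the truth. Samples that could show a change are already drawn, but no parameter definition directs the analyst to them.

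**Working it through.** **Timing (protocol Table 2)**

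| Day 6-7 sample | Time (h) | Relative to tablet at 120 h |
|---|---|---|
| Day 6 predose | 118.5 | 1.5 h before |
| 1 h | 119.5 | 0.5 h before |
| 2 h, end of infusion | 120.5 | 0.5 h after |
| 4 h | 122.5 | 2.5 h after |
| 6 h | 124.5 | 4.5 h after |
| 8 h, before second infusion | 126.5 | 6.5 h after |
| Day 7 predose | 142.5 | 22.5 h after |

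Three samples could be called the Day 6 trough: 118.5, 126.5 and 142.5 h. Only the last two follow the tablet.

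**Model inputs.** 500 mg over 2 h every 8 h (protocol 3.4.1 and 3.4.5); clearance about 5 L/h and half-life 3-4 h (protocol 1.1.1.1). The documents give no size for any pitavastatin effect, so a 20% fall in clearance is assumed, starting at the tablet or 1 h later.

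**Baseline, one compartment at steady state.** Infusion rate R = 250 mg/h, R/CL = 50 mg/L, k = ln2/t1/2.
- C(0) = 50(1 − e^(−2k))e^(−6k)/(1 − e^(−8k)). For t1/2 = 3 h, k = 0.231 and C(0) = 50 × 0.370 × 0.250/0.8425 = 5.49 mg/L.
- C(2) = 5.49 × 0.630 + 50 × 0.370 = 21.96 mg/L.
- AUC0-8h = 500/5 = 100 mg·h/L.
- AUC(0-1.5 h) = 50 × 1.5 − (50 − C(0))(1 − e^(−1.5k))/k = 75 − 44.51 × 1.268 = 18.6. At t1/2 = 4 h it is 18.1.

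So 18-19% of AUC0-8h accrues before the tablet and 81-82% after it.

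**Clearance × 0.8 from the tablet, t1/2 = 3 h**
- C(1.5) = 5.49 × 0.707 + 50 × 0.293 = 18.53.
- C(2) = 62.5 − (62.5 − 18.53)e^(−0.5 × 0.8 × 0.231) = 22.41, so the C_max ratio is 22.41/21.96 = 1.02.
- 8-h ratio = 1.0204 × e^(0.2 × 6 × 0.231) = 1.35.

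**Day 6/Day 5 ratios for t1/2 3-4 h**

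| Parameter | Effect from tablet | Effect 1 h later |
|---|---|---|
| Predose concentration | 1.00 | 1.00 |
| C_max (2 h) | 1.02 | 1.00 |
| AUC0-8h | 1.08-1.10 | 1.05-1.07 |
| AUC2-8h | 1.11-1.14 | 1.07-1.09 |
| 8-h concentration | 1.25-1.35 | 1.21-1.29 |

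If clearance were lower throughout, AUC over the interval would rise by 1/0.8 = 1.25. AUC0-8h therefore keeps between ln(1.054)/ln(1.25) = 24% and ln(1.101)/ln(1.25) = 43% of that effect on the log scale. The 1.25 is only a reference, since one tablet may not sustain an effect. Even if clearance halved at the tablet, C_max would rise only 4-5%.

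**k_el and t1/2.** SAP 8.2 requires at least three terminal points excluding C_max, which leaves 4, 6 and 8 h, all after the tablet. In the model their slope recovers the full 0.80. But the window is 8 − 4 = 4 h, and the SAP calls k_el unreliable when the window is shorter than twice t1/2, here 6-8 h. To pass, t1/2 would have to be 2 h or less. The SAP's point-count sentence mentions single dosing, but its reliability sentence has no such limit, so its application to ceftobiprole should be stated.

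**The case against.** The other side has good points, and most of them stand.

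- A reader might infer that the Day 6 parameters as a group are settled before the tablet. They are not: over 80% of AUC0-8h accrues afterwards, and k_el and t1/2 come entirely from later samples.
- A reader might infer that both reported troughs are pre-tablet by definition. The documents do not say so. Footnote j also calls the Day 6 8-h sample a predose sample, and protocol 3.5.2.1 gives morning pre-infusion samples a separate rule from trough samples. The 8-h reading is at least as available. What stands is that the choice is open and one reading makes the comparison empty.
- The 8-h and Day 7 concentrations will be tabulated under SAP 8.1, so the information is not lost. It is only not presented as a comparison.
- A reader might infer a biased test. SAP section 4 excludes formal testing, and no ratio, interval or model is planned for ceftobiprole. The documents do not say that similar values will be reported as no effect.
- Protocol 1.1.1.1 attributes elimination mainly to glomerular filtration, so a large effect of pitavastatin is not expected.
- AUC2-8h gains little over AUC0-8h. That is true in the table above. The 8-h concentration is the more responsive measure.

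The k_el point does not fully rescue the plan: at the protocol's half-life, the most responsive listed parameters fall under the SAP's own unreliable label. V_z rests on k_el, and CL, if taken as dose over AUC0-8h, shares that dilution.

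**Conclusion.** The point holds as a matter of definition and interpretability for one descriptive secondary objective. Timing alone makes a Day 6 predose C_trough uninformative about pitavastatin and end-of-infusion C_max and t_max barely informative. AUC0-8h is attenuated toward no difference, keeping roughly a quarter to two fifths of the assumed effect on the log scale. C_trough is not assigned to a sample, and the Day 7 predose sample enters no parameter.

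The timing results need only Table 2. The sizes rest on a one-compartment model, a half-life of 3-4 h and an illustrative 20% fall in clearance. They compare how responsive the parameters are and do not predict an effect. The pitavastatin and coproporphyrin I analyses are unaffected.

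**What to change.** In SAP 8.2 and protocol Table 3:

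1. Define the troughs with pitavastatin as the Day 6 8-h sample, compared with the Day 5 8-h sample, and the Day 7 predose sample, compared with the Day 6 predose sample at the same clock time.
2. Report AUC2-8h for Day 5 and Day 6 beside AUC0-8h.
3. State that Day 6 predose C_trough is not informative, and Day 6 C_max and t_max are barely informative, on pitavastatin's effect.

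While editing, say whether the rule of twice the half-life applies to ceftobiprole k_el and how values failing it will be shown.

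The cost is SAP and table wording and a few more descriptive rows. Every sample is already scheduled, so dosing, visits and blood volume do not change.

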8.3 Exposure parameters of CP-I

Plasma exposure parameters of CP-I will be estimated using similar methods than PK parameters. Estimated plasma exposure parameters of CP-I are: C_{max}, t_{max}, C_{through}, C_{25.5h}, AUEC_{0-25.5h}. In addition, C_{max}, AUEC_{0-25.5h}, C_{through} and C_{25.5h} ratios between Days 5 to 6/Days -1 to 1, and shift (if any) of t_{max} on Days 5 to 6 versus Days -1 to 1 will be calculated.

All PD parameters will be summarized with descriptive statistics (n, mean, SD, CV, minimum, median, maximum, geometric mean, and geometric CV) for the PD set. For t_{max}, only median, minimum and maximum will be presented. All parameters will be listed by subject and period. Parameters that meet the inclusion criteria for PD analysis will be accompanied by an indication that each criteria is met.

A scatter plot of individual (plus mean and median) PK parameters C_{max}, AUC_{0-25.5h}, AUC_{0-t}, and C_{through} by treatment for CP-I will be provided, as appropriate.

A mixed-effects model with subject as a random effect and treatment (i.e. without or with ceftobirpale) as a fixed effect will be performed on the following natural logarithm (ln)-transformed PD parameters of CP-I: C_{max} and AUEC_{0-25.5h}. From this model, the back-transformed least-squares means (LSMeans) for each treatment will be presented. The ratio of least-squares geometric means between the test treatment (coadministration of pitavastatin + ceftobiprole) to the reference (pitavastatin alone) and the corresponding 90% CI will be presented.

